### **8.2.5.1 Statistical Methods for Efficacy Analyses**

For the primary efficacy endpoint independently reviewed ORR using RECIST 1.1, the point estimate, 97.5% confidence interval, and p-value for testing ORR is greater than the

historical control rate of 5% will be provided separately for all subjects and PD-L1 strong positive subjects using exact binomial distribution. Subjects in the primary analysis population (FAS) without response data will be counted as non-responder.

Efficacy for the key secondary endpoint of ORR among PD-L1 positive subjects, as well as other secondary analyses of ORR using modified RECIST 1.1 and ORR among subjects with HPV positive head and neck cancer will be evaluated in the same manner as in the primary analysis.

For the secondary analyses of response duration, PFS and OS, Kaplan-Meier (KM) curves and median estimates from the KM curves will be provided as appropriate. Subjects without efficacy evaluation data or without survival data will be censored at Day 1.

The primary analysis for each hypothesis will be conducted after all subjects have at least 6 months of follow-up. The final analysis of OS will occur when <5% of patients remain on study drug.

**Table 10** summarizes the key efficacy analyses.

Table 10      Analysis Strategy for Key Efficacy Variables

Endpoint	Statistical Method	Analysis Population	Missing data approach
ORR • RECIST 1.1, independent radiology review	Exact test of binomial parameter	FAS in all below populations: 

• all-comers

• PD-L1 strong positive*

• PD-L1 positive‡

	Subjects with missing data are considered non-responders
ORR • RECIST 1.1, independent radiology review • modified RECIST 1.1, independent radiology review • modified RECIST 1.1, investigator	Point estimate and exact binomial CI	FAS in all below populations: 

• all-comers

• PD-L1 strong positive*

• PD-L1 positive‡

• HPV positive

 APaT in all below populations: 

• all-comers

• PD-L1 strong positive

• PD-L1 any positive

• HPV positive

	Subjects with missing data are considered non-responders
Response Duration • RECIST 1.1, independent radiology review • modified RECIST 1.1, investigator	Summary statistics using Kaplan-Meier method	FAS in all below populations: 

• all-comers

• PD-L1 strong positive*

• PD-L1 positive‡

 APaT in all below populations: 

• all-comers

• PD-L1 strong positive

• PD-L1 positive

	Non-responders are excluded in analysis

Endpoint	Statistical Method	Analysis Population	Missing data approach
PFS 
 
RECIST 1.1, independent radiology review
 
modified RECIST 1.1, investigator
 
	Summary statistics using Kaplan-Meier method	FAS in all below populations: 
 
all-comers
 
PD-L1 strong positive*
 
PD-L1 positive‡
 
 APaT in all below populations: 
 
all-comers
 
PD-L1 strong positive
 
PD-L1 positive
 
	Censored at last assessment date
OS 
 
RECIST 1.1, independent radiology review
 
modified RECIST 1.1, investigator
 
	Summary statistics using Kaplan-Meier method	FAS in all below populations: 
 
all-comers
 
PD-L1 strong positive*
 
PD-L1 positive‡
 
 APaT in all below populations: 
 
all-comers
 
PD-L1 strong positive
 
PD-L1 positive
 
	Censored at last assessment date

\* PD-L1 strong positive is defined as PD-L1 tumor proportion score  $\geq 50\%$  by IHC.  
 ‡ PD-L1 positive is defined as PD-L1 tumor proportion score exceeding 0% by IHC.  
 ¶ Exact Clopper-Pearson 95% CI will be provided.

Exploratory analyses of PFS using modified RECIST 1.1 criteria and PFS/OS by exploratory candidate biomarkers will also follow the same approach as for the secondary analyses of PFS and OS. The exploratory analysis of ORR by PD-L1 combined positive score (CPS) and exploratory candidate biomarkers will be conducted using point estimate and exact binomial CI.

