### 3.3 Exploratory Objectives

- 1) **Objective:** To estimate the progression-free survival (PFS) using modified RECIST 1.1 by independent radiology review in subjects receiving pembrolizumab (MK-3475) with recurrent and/or metastatic head and neck squamous cell carcinoma who have progressed on platinum and cetuximab therapy.
- 2) **Objective:** To estimate ORR using RECIST 1.1 assessed by independent radiology review in subjects with PD-L1 combined positive score  $\geq 1\%$  recurrent and/or metastatic head and neck squamous cell carcinoma who have progressed on platinum and cetuximab therapy.

3) **Objective:** To investigate the relationship between candidate efficacy/resistance biomarkers and anti-tumor activity of pembrolizumab (MK-3475) utilizing pre-treatment tumor biopsies and blood sampling.

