**Transcriptional Analyses**

Messenger RNA (mRNA) expression profiling in archival material (biopsy specimens, peripheral blood) will be completed to assess expression of approximately 700 genes and attempt to define a gene set critical for clinical response to pembrolizumab (MK-3475). The hypothesis to be tested is that pembrolizumab (MK-3475) induces responses in tumors that reflect an inflamed/ immune phenotype based on gene expression signatures capturing PD-L1 & interferon-gamma transcriptional programs. Global profiling will also be pursued. Expression of individual genes related to the immune system may also be evaluated such as immune signatures and critical cytokines (e.g., IL-10).

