## **8.2.5 Statistical Methods**

Statistical testing and inference for safety analyses are described in 8.2.5.2. Efficacy results that will be considered to be statistically significant after consideration of the strategy for controlling the Type I error are described in Section 8.2.6, Multiplicity. Nominal p-values may be computed for other efficacy analyses as a measure of strength of association between the endpoint and the treatment effect rather than formal tests of hypotheses.

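### The exploratory biomarker objective asks for an association with response, but Section 8.2.5.1 provides only per-group summaries; a short addition would close the gap

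*Combined protocol and SAP*

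**What the plan says.** Section 3.3, objective 3, reads: "To investigate the relationship between candidate efficacy/resistance biomarkers and anti-tumor activity of pembrolizumab (MK-3475) utilizing pre-treatment tumor biopsies and blood sampling". Section 4.2.3.3 (Transcriptional Analyses) commits to expression profiling "to assess expression of approximately 700 genes and attempt to define a gene set critical for clinical response" and adds: "The hypothesis to be tested is that pembrolizumab (MK-3475) induces responses in tumors that reflect an inflamed/ immune phenotype based on gene expression signatures".

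The method is in Section 8.2.5.1. Response rate by PD-L1 combined positive score and "exploratory candidate biomarkers will be conducted using point estimate and exact binomial CI". For the time-to-event endpoints, "PFS/OS by exploratory candidate biomarkers will also follow the same approach as for the secondary analyses of PFS and OS", and that approach is that "Kaplan-Meier (KM) curves and median estimates from the KM curves will be provided as appropriate".

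Cut-points are given only for PD-L1: tumor proportion score above 0% and at least 50%, and combined positive score at least 1%. Section 8.0 says that no separate SAP will be issued.

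**The concern.** A relationship between a marker and response is a contrast: an odds ratio, a difference in rates, a hazard ratio. A response rate with its interval in one group, or a Kaplan-Meier median in one group, is not a contrast, and two of them side by side leave the comparison to the reader. A marker measured on a continuous scale, such as an expression signature, must also be cut before either summary can be produced, and the plan fixes no cut for any such marker other than PD-L1.

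Two things are at stake. One is efficiency, because responders will be few and cutting a graded marker discards information. The other is credibility: response data are open-label, so a cut-point or signature chosen after markers are linked to outcome can be tuned to the data. The primary hypotheses, their type I error control and the safety analyses are not affected.

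**Working it through.** **1. Is an association method stated anywhere else?**

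- Section 8.2.5 allows nominal p-values, but "as a measure of strength of association between the endpoint and the treatment effect rather than formal tests of hypotheses". That concerns treatment effect, not marker against response.
- Section 8.2.5.3.2 covers exposure-response from PK data. It is optional and reported separately.
- Section 8.2.8 lists categories (HPV, PD-L1 cut-offs, ECOG status, prior therapies) without a contrast.
- Section 4.1.3 intends to correlate PD-L1 with outcome under two cut-offs and names no method.

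So Section 8 gives no odds ratio, hazard ratio, difference, regression or marker-level multiplicity rule.

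**2. The plan's own design figure.** No power figure is given for the biomarker objective, so the primary one supplies the scale. With X binomial, n = 135 and p = 0.05, P(X ≥ 14) = 0.0079 and P(X ≥ 13) = 0.0181, so the rule of 14 responses at one-sided 1.25% reproduces. The alternative is redacted. A response rate of 13% gives P(X ≥ 14) = 0.851, matching the stated 85%, so 13% is back-solved and is an assumption. As an upper value I use 18%, close to the pooled rate in the earlier-trial PD-L1 data of Section 4.1.3: (5 + 5)/(11 + 44) = 10/55 = 18.2%. Expected responders are 135 × 0.13 = 17.6 to 135 × 0.18 = 24.3.

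**3. What a contrast adds, on the documents' own counts.** Section 4.1.3 reports 5/11 responders with high PD-L1 and 5/44 with low.

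- Output as planned: 45.5% (exact 95% CI 16.7 to 76.6) and 11.4% (3.8 to 24.6).
- Output with a contrast: difference 45.5 − 11.4 = 34.1 points (Newcombe 95% CI 6.8 to 61.4); conditional odds ratio 6.2 (95% CI 1.1 to 37.4); Fisher p = 0.019.

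Only the second states how large the relationship is and how uncertain. That cut was derived by the Youden index, so its size may be optimistic; the example shows the form of the output and is not evidence about the marker.

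**4. Illustrative power for one continuous marker.** Assumptions: n = 135 with a marker result for every subject, standard normal marker x, logit P(response) = a + b·x with b = log(odds ratio per SD), two-sided 5%, 1,500 replicates.

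| Response rate | Odds ratio per SD | Logistic, continuous | Median split, Fisher |
|---|---|---|---|
| 13% | 1.0 (type I error) | 5.4% | 2.9% |
| 13% | 1.5 | 37% | 22% |
| 13% | 2.0 | 74% | 50% |
| 18% | 1.0 (type I error) | 5.7% | 3.6% |
| 18% | 1.5 | 42% | 27% |
| 18% | 2.0 | 85% | 63% |

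Repeat runs differ by one or two points. A small part of the gap is Fisher's conservatism: at odds ratio 2.0 an uncorrected chi-square test on the same split reaches 52% and 66%.

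**5. The same comparison when the effect is a step.** With 20% of subjects marker-high and response rates 45.5% against 11.4%, power is about 81% continuous, 95% for Fisher at the true cut and 52% for a median split. With 81.1% positive and rates 21.5% against 4% (the combined-positive-score figures in Section 4.1.3), it is about 28%, 56% and 15%. A correct, known cut beats the continuous model here; a median split does not.

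**6. Gene-level screen.** If about 700 unrelated genes were each tested at nominal 5%, 700 × 0.05 = 35 would be expected to cross by chance. This matters only once gene-level tests are run.

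**The case against.** The objective is exploratory, and Section 8.0 lets exploratory analyses change after finalization if the study report says when and why. A reader might infer that the trial cannot test the expression hypothesis at all. The documents do not support that: nothing bars a later regression. What stands is that the plan as written offers only an informal side-by-side reading.

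A reader might also assume that every candidate marker is continuous. HPV and PD-L1 are used as categories, and parts of Section 4.2.3.3 (a hypermutated state, dominant T-cell clones, genetic variation) can be read as categories and are worded as possibilities. For those, a rate with an exact interval is a reasonable description; it lacks only the contrast.

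A third tempting reading is that markers would be judged by whether two confidence intervals overlap. The plan states no such rule, so no loss can be charged to it on that basis. Nor does the plan itself generate 35 false positives, since it specifies no gene-level tests.

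Finally, the simulation in step 4 fits the model that generated the data, which favors the continuous analysis. Step 5 shows that the ranking can reverse. This stands, and is why the cut-off summaries should stay.

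The statement in Section 12.2 that a main-trial expression analysis is detailed in Section 8.0 adds little: it sits in the specimen appendix and concerns specific analyses, whereas objective 3 is general.

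**Conclusion.** The mismatch is real and can be seen on the page: the aim is a relationship, and the stated methods are one-group summaries that need cut-points which the plan defines only for PD-L1. It is a worthwhile low-cost improvement, not a defect in the trial's main conclusions.

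The size is illustrative. Under a linear-logit effect with odds ratio 2.0 per SD, n = 135 and response rates of 13-18%, power is about 73-86% with the marker continuous and about 50-63% with a median split and Fisher's test. The response rate, effect size, marker distribution and complete marker data are all assumed, and the figures are for one marker at two-sided 5%, not under false-discovery control. The case for an association measure does not depend on them.

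**What to change.** In Section 8.2.5.1 keep the present sentences. One of them also carries the method for PFS by modified RECIST 1.1, and the summaries by cut-off remain useful as description. Add:

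1. **Association measures.** For markers on a continuous scale, such as the expression signature: logistic regression of independently reviewed response on the marker, on one scale named in advance, reporting the odds ratio per SD with 95% CI; Cox regression on the same scale for PFS and OS. For markers used as categories (PD-L1 cut-offs, HPV): the difference in response rates or the odds ratio, and the hazard ratio, each with 95% CI.
2. **Order.** The interferon-gamma/PD-L1 signature is fixed before marker data are linked to outcome, and is tested first.
3. **Screening.** Any gene-level screen uses false-discovery-rate control.

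State that all of this is exploratory and outside the alpha scheme of Section 8.2.6. The cost is a little more analysis work and some plan wording, and the scale for each continuous marker must be settled in advance. No new subjects, samples or procedures are needed.

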### 8.2.5.2 Statistical Methods for Safety Analyses

Safety and tolerability will be assessed by clinical review of all relevant parameters including adverse experiences (AEs), laboratory tests, and vital signs.

Summary statistics (counts, percentage, mean, standard deviation, etc.) will be provided for the safety endpoints as appropriate. The 95% confidence interval for the incidence rate of Grade 2 or higher adverse events with an immune etiology and the incidence rate of Grade 4/5 AEs will be provided as appropriate.

### 8.2.5.3 Summaries of Baseline Characteristics, Demographics, and Other Analyses

#### 8.2.5.3.1 Demographic and Baseline Characteristics

Baseline characteristics will be assessed by the use of tables and/or graphs. No statistical hypothesis tests will be performed on these characteristics. The number and percentage of subjects screened, randomized, the primary reasons for screening failure, and the primary reason for discontinuation will be displayed. Demographic variables (e.g., age, gender), baseline characteristics, primary and secondary diagnoses, and prior and concomitant therapies will be summarized by treatment either by descriptive statistics or a categorical summary.

### 8.2.5.3.2 Pharmacokinetic Analyses

Based on pharmacokinetic data obtained within this study, the exposure response relationship for MK-3475 and measures of antitumor activity/efficacy and pharmacodynamic biomarkers may be explored. The analysis, if performed, will be reported separately.

### 8.2.6 Multiplicity

The false positive rate for testing the primary efficacy hypotheses is controlled at 2.5% (1-sided) with 1.25% allocated to all subjects and 1.25% allocated to PD-L1 strong positive subjects. The key secondary efficacy hypothesis of ORR based on RECIST 1.1 assessed by independent radiology review in PD-L1 positive subjects will be tested at 1.25% (one-sided) if the primary efficacy hypothesis in PD-L1 strong positive subjects is rejected. If both the primary hypothesis for PD-L1 strong positive subjects and the key secondary efficacy hypothesis are rejected, the additional alpha level 1.25% will be allocated back to all subjects and the primary efficacy hypothesis for all subjects will be tested at 2.5% (Figure 2).

[figure not shown]

Figure 2 Multiplicity Strategy

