### 3.0 OBJECTIVE(S) & HYPOTHESIS(ES)

#### 3.1 Primary Objective(s) & Hypothesis(es)

- 1) **Objective:** To determine the safety and tolerability of 200 mg Q3W dose of pembrolizumab (MK-3475) in subjects with recurrent and/or metastatic head and neck squamous cell carcinoma who have progressed on platinum and cetuximab therapy.
- 2) **Objective:** To evaluate anti-tumor activity of pembrolizumab (MK-3475) by objective response rate (ORR) using RECIST 1.1 assessed by independent radiology review in subjects with recurrent and/or metastatic head and neck squamous cell carcinoma who have progressed on platinum and cetuximab therapy.

**Hypothesis:** Intravenous administration of single agent pembrolizumab (MK-3475) to subjects with recurrent and/or metastatic head and neck squamous cell carcinoma who have progressed on platinum and cetuximab therapy will result in a clinically meaningful ORR of greater than 5% based on RECIST 1.1 by independent radiology review.

- 3) **Objective:** To evaluate anti-tumor activity of pembrolizumab (MK-3475) by ORR using RECIST 1.1 assessed by independent radiology review in subjects with PD-L1 strong positive recurrent and/or metastatic head and neck squamous cell carcinoma who have progressed on platinum and cetuximab therapy.

**Hypothesis:** Intravenous administration of single agent pembrolizumab (MK-3475) to subjects with PD-L1 strong positive recurrent and/or metastatic head and neck squamous cell carcinoma who have progressed on platinum and cetuximab therapy will result in a clinically meaningful ORR of greater than 5% based on RECIST 1.1 by independent radiology review.

The study can be declared successful in the respective population or subpopulation if *either* the hypothesis test for objective (2) or the hypothesis test for objective (3) is significant.

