#### 8.1.1 Efficacy Analyses

The full analysis set (FAS) population (defined as all subjects with a baseline scan with measurable disease by independent radiology review who receive at least one dose of study treatment) will serve as the primary population for the analyses of efficacy data in this trial. Supportive analyses of efficacy will be conducted in the all Patients as Treated (APaT) population as well as the FAS. Objective response rate will be used to evaluate the primary efficacy hypotheses and will be estimated separately for all subjects and for subjects who are PD-L1 strong positive, where PD-L1 strong positive is defined as PD-L1 tumor proportion score greater than or equal to 50% by IHC. A 97.5% confidence interval along with a one-sided p-value for testing the null hypothesis based on the binomial distribution will be provided for ORR. The respective study is considered to have reached the efficacy objective if the p-value for testing the primary hypothesis in all subjects is less than 1.25% OR if the p-value for testing the primary hypothesis in PD-L1 strong positive subjects is less than 1.25%. A stepdown procedure controls Type I error between the primary PD-L1 strong positive hypothesis and the secondary PD-L1 positive hypothesis. An outline of the efficacy analysis strategy is presented in [Table 9](#) below.

Table 9 Primary Analysis Strategy for Efficacy Endpoints

Endpoint/Variable ‡ (Description, Time Point)	Statistical Method	Analysis Population	Missing Data Approach
Primary:			
ORR (RECIST 1.1) based on independent radiology review	Exact test of binomial parameter	FAS	Subjects with missing data are considered non-responders
ORR (RECIST 1.1) in PD-L1 strong positive subjects* based on independent radiology review	Exact test of binomial parameter	FAS	Subjects with missing data are considered non-responders
Secondary:			
ORR (RECIST 1.1) in PD-L1 positive subjects† based on independent radiology review	Exact test of binomial parameter	FAS	Subjects with missing data are considered non-responders
Response Duration based on independent radiology review	Summary statistics using Kaplan-Meier method	All responders	Non-responders are excluded in analysis
Response Duration in PD-L1 strong positive subjects based on independent radiology review	Summary statistics using Kaplan-Meier method	All responders among PD-L1 strong positive* subjects	Non-responders are excluded in analysis

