### 8.2.7 Sample Size and Power Calculations

Assuming that approximately 135 of the 150 enrolled subjects with recurrent and/or metastatic head and neck cancer will be evaluable for the primary efficacy analysis in the FAS population, the study has approximately 85% power to demonstrate that the ORR is  $>5\%$  with a type I error rate of 1.25% [28]. Success for this hypothesis requires at least 14/135 responses. The null ORR rate of 5% was determined based on a prior randomized trial of methotrexate therapy vs. gefinitib in a second line population in which an ORR of 4% was observed in the methotrexate arm [28].

The proportion of subjects who are PD-L1 strong positive among the 150 subjects enrolled is not known but is estimated to be approximately 20%~30%, then 150 subjects would be expected to provide 30~45 PD-L1 strong positive subjects with recurrent and/or metastatic head and neck cancer will be evaluable for the primary efficacy analysis in the FAS population. [Figure 3](#) shows the power curve ranging about 92% to 99% vs the sample size between 30 and 45, when the ORR $>5\%$  with a type I error rate of 1.25% [28]. Success for this hypothesis requires at least 6 responses out of 30~39 subjects with PD-L1 strongly positive, and at least 7 responses out of 40~45 subjects with PD-L1 strongly positive. The power may increase or decrease depending on the actual number of PD-L1 strong positive subjects who are enrolled in the study ([Figure 3](#)).

[figure not shown]

Figure 3 Power Curve vs Sample Size of PD-L1 Strong Positive Subjects

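### The text of 8.2.6 recycles alpha in one direction only; passing the all-subjects 1.25% on to the PD-L1 strong positive test would keep the 2.5% familywise rate and add a little power

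*Combined protocol and SAP*

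**What the plan says.** Section 8.2.6 (Multiplicity) sets the total and the split: "The false positive rate for testing the primary efficacy hypotheses is controlled at 2.5% (1-sided) with 1.25% allocated to all subjects", with "1.25% allocated to PD-L1 strong positive subjects".

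It then describes two transfers:
- The PD-L1 positive hypothesis, the key secondary, "will be tested at 1.25% (one-sided) if the primary efficacy hypothesis in PD-L1 strong positive subjects is rejected".
- If strong positive and PD-L1 positive are both rejected, "the additional alpha level 1.25% will be allocated back to all subjects", which is then tested at 2.5%.

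No sentence says what happens to the all-subjects 1.25% when the all-subjects hypothesis is rejected first. The section refers to Figure 2 for the strategy, and that figure is not visible in the text available.

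Section 8.1.1 gives a single success level for strong positive ("if the p-value for testing the primary hypothesis in PD-L1 strong positive subjects is less than 1.25" percent). The cut-offs in 8.1.3 and 8.2.7 match that level: 6 responses for 30-39 subjects and 7 for 40-45. Under Section 3.1 the study succeeds if either "the hypothesis test for objective (2) or the hypothesis test for objective (3) is significant".

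**The concern.** The plan already recycles alpha, so it is not a plain Bonferroni split; one link of the loop is simply not described. The missing link applies when all subjects is rejected, which is the outcome the trial is sized for (about 85% power). In that event the text leaves 1.25% unused and keeps strong positive at 1.25%, although it could be tested at 2.5% within the same familywise limit.

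Strong positive is one of the two primary efficacy hypotheses and also the gate to the PD-L1 positive test. At stake is the power to add those two claims to a success in all subjects.

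**Working it through.** **Inputs from the documents.** Null ORR 5% (8.2.5.1). Evaluable subjects: "approximately 135 of the 150 enrolled subjects" (8.2.7). All-subjects cut-off 14/135 with about 85% power. Strong-positive prevalence 20-30%, giving n=30-45, with about 92% to 99% power.

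**Assumptions.** The alternative ORRs are redacted. An all-subjects ORR of 13% reproduces the stated 85% (85.1%). A strong-positive ORR of 30% reproduces the stated range (92.3% at n=30, 99.2% at n=45). ORRs of 25% and 20% are sensitivity cases; at n=30 they give 79.7% and 57.2% power, so they are not the planning value.

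**Step 1: reproduce the plan's cut-offs.** Take the smallest r with P(X ≥ r) < 1.25% for X ~ Bin(n, 0.05). This gives r=6 for every n from 30 to 39, r=7 for every n from 40 to 45, and r=14 for n=135 (exact level 0.79%). All agree with 8.2.7.

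**Step 2: cut-offs at 2.5%.**

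| n | r at 1.25% | r at 2.5% |
|---|---|---|
| 30-33 | 6 | 5 |
| 34-39 | 6 | 6 |
| 40-45 | 7 | 6 |

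The cut-off moves at 4 + 6 = 10 of the 16 planned sizes.

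**Step 3: error control with the loop closed.** At every stage the levels of the hypotheses not yet rejected sum to no more than 2.5%, so the familywise rate is held (a standard Bonferroni-based graphical procedure). If all the nulls are true, the first primary rejection must use the initial 1.25% levels. The chance of any primary rejection is therefore the same with or without the added step: 1.06% at n=30, 1.85% at n=39, 1.32% at n=45. If the strong-positive null is true but the all-subjects null is false, the maximum strong-positive error over n=30-45 rises from 1.23% (n=39) to 2.39% (n=45).

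**Step 4: power gain.** Let X ~ Bin(n, ps) be responses among strong-positive subjects and Y ~ Bin(135−n, pr) those among the others, with pr = (135 × 0.13 − n × ps)/(135 − n). Only the one count between the two cut-offs matters, and only if all subjects succeeds:

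gain = P(X = r at 2.5%) × P(X + Y ≥ 14 given that X)

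Example, ps=30%, n=30: pr = (17.55 − 9)/105 = 8.14%; P(X=5) = 0.0464; P(Y ≥ 9) = 0.487; the product is 0.0226.

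| ps | n | Power now | Loop closed | Gain (points) |
|---|---|---|---|---|
| 30% | 30 | 92.3% | 94.6% | 2.3 |
| 30% | 34-39 | – | unchanged | 0 |
| 30% | 40 | 97.6% | 97.9% | 0.3 |
| 30% | 45 | 99.20% | 99.23% | 0.03 |
| 25% | 30 | 79.7% | 86.9% | 7.2 |
| 25% | 40 | 90.4% | 93.0% | 2.6 |
| 20% | 30 | 57.2% | 71.5% | 14.3 |
| 20% | 40 | 71.4% | 80.8% | 9.3 |

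Gains are taken before rounding.

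**Step 5: sensitivity to subgroup size and to the other subjects' ORR.** Fix the ORR in the other subjects at 10% and average over n ~ Bin(135, prevalence). For a strong-positive ORR of 30% the gain is 2.0, 1.1 and 0.5 points at 20%, 25% and 30% prevalence. For 20% it is 5.6, 5.1 and 4.2 points.

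**Step 6: interval and test.** With 5/30 responses the exact 97.5% CI has a lower limit of 4.7%, below the null of 5%, although the 2.5% test rejects (p = 1.56%). The 95% CI has a lower limit of 5.6%, which agrees with the test.

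**The case against.** Most of the case for leaving the plan alone is sound, and it limits the weight of this point.

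- **Validity.** A reader might infer that the multiplicity scheme is faulty. It is not. The procedure as written controls 2.5%, nothing in the documents requires all alpha to be used, and sending recycled alpha to all subjects is a legitimate choice.
- **Study success.** A reader might infer that the trial gives up some chance of succeeding. It does not. The extra alpha is available only after all subjects has been rejected, and under Section 3.1 that is already success.
- **Error control.** It is tempting to say the one-way rule protects nothing. It does not protect the familywise rate, but it does hold the strong-positive test's own error lower when that null is true and the all-subjects null is false. The plan sets no separate requirement on that error, and 2.39% is still under 2.5%.
- **Missing figure.** The documents do not establish that the alpha is never passed on. Figure 2 may show the step. Section 8.1.1 is weak evidence either way, because it also omits the 2.5% level that 8.2.6 allows for all subjects.
- **Size.** At the ORR implied by the stated power, the gain is zero or a fraction of a point at most planned sizes.

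What remains is that the change adds power without taking any from another hypothesis, and adds most when the strong-positive effect is smaller than planned.

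**Conclusion.** The point holds as an optional gain in efficiency, not as an error. The text of 8.2.6 leaves the loop open, and closing it can only add rejections while keeping the familywise 2.5%. The benefit is confined to the strong-positive claim and the PD-L1 positive test it gates. At the back-solved strong-positive ORR of 30% it is at most about 2 points within n=30-45. At 25% or 20% it reaches 7.2 or 14.3 points at n=30. These sizes rest on assumed ORRs (13% overall, and 30%, 25% or 20% in strong positive) and on 135 evaluable subjects. The statement about the text is subject to a check of Figure 2.

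**What to change.** Check Figure 2 first. If it already shows the step from all subjects to strong positive, bring the text into line with it. Otherwise, make these changes by protocol amendment:

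1. In 8.2.6 and Figure 2: if the all-subjects hypothesis is rejected at 1.25%, its alpha passes to the strong-positive hypothesis, tested at 2.5%, and on rejection to the PD-L1 positive hypothesis, tested at 2.5%.
2. In 8.1.1: align the p-value rule, including the 2.5% level that 8.2.6 already allows for all subjects.
3. In 8.1.3 and 8.2.7: state the conditional strong-positive cut-offs (5 for n=30-33, 6 for n=34-45) beside the present ones.
4. In 8.1.1 and 8.2.5.1: report a 95% CI alongside the 97.5% CI for any hypothesis tested at 2.5%, so that interval and test agree.

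Section 8.0 issues no separate SAP and calls for an amendment when methods for primary hypotheses change before PD-L1 status is obtained. The change should be made only in that window. The cost is one amendment touching several sections, with no added subjects or data. The statistical price is the higher ceiling on the strong-positive test's own error (2.39% against 1.23%).
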